To compare the clinical effectiveness of a self-contained bagged larval debridement therapy (intervention) (BioBag) with bedside sharp debridement (control). The following comparisons will be made: 1) The visual reduction of non-viable tissue in the wound bed of chronic full-thickness lower extremity or diabetic foot ulcers, and 2) The reduction in colony forming units (CFU) of bacterial biofilm in samples taken from the wound bed.

Specific Aim 2

To compare wound characteristics (e.g., inflammatory markers, wound size) in the intervention group (BioBag therapy) and control group (Sharp debridement) over time.

Specific Aim 3

To investigate patient, caregiver and clinician perceptions of larval therapy dressings and bedside sharp debridement using measures of self-reported aesthetics, ease of use, and wound pain.

6. Research Plan:

Research design and methods

Design: A repeated measures, randomized control trial experimental design will be used for this study. Subjects will serve as their own control, in addition to a control group. Initial wound samples will be followed by two subsequent repeated wound samplings approximately four days apart. Informed consent will be obtained prior to all procedures, photo consents will also be obtained for wound photos.

Veteran Site: North Florida South Georgia Veterans Health System

Setting, Sample: A target goal final sample size of one hundred twenty eight adults from the North Florida South Georgia VHS will be recruited (total recruited number anticipated to be ~140 allowing for 10% attrition). Including target of 128 Caregivers and 6 Providers, and accounting for 12 caregivers lost to follow up or 10 subjects who fail screening, the total study recruitment population is 296. Wound providers and clinicians who care for lower extremity or diabetic foot ulcers will be provided with a "Provider Study Flyer" which gives a brief description of the study with inclusion/exclusion criteria listed (to remind the Provider to approach potentially eligible patients with Research Team Contact

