information). The clinicians will also be asked to make a Recruitment Brochure available to potentially eligible patients (those with lower extremity or diabetic foot ulcers over 8 weeks duration). In addition, study flyers will be sent to select VA wound and podiatry offices in the NF/SG VHS. Providers will be asked to contact study team if any patient is willing to hear about the study. If the patient is willing to hear about the study, they may contact a study team member from the contact number on the recruitment brochure or the provider can let the patient know when the research team member is scheduled to be in the provider clinic office and the patient may talk directly to the research study team member for more information. If patients call a research team member, they will have their questions answered but will not be screened over the phone. They will be scheduled to come into the provider office to discuss the study with a research team member and review informed consent. Members of the research study team will review the informed consent with the patient and enroll the subject if they agree to participate. Wound clinicians will not be asked to consent subjects, or to provide a list of patients or appointment times to research team. However, the subject's wound providers (clinicians) will be the ones to perform the sample collection and apply the LDT or bedside sharp debridement. The sample also includes one available caregiver of the patient (non-professional) to answer the caregiver surveys if willing, and the wound care providers, who will be asked to answer the clinician survey regarding perceptions of debridement methods.

Sample Size Power Analysis: Power analysis is based on the patient sample and the primary study aim of comparing debridement methods on clinical effectiveness. The POWER procedure in SAS version 9.2 (Cary, N.C.) was used to conduct the power analysis. Assuming a Type I error rate of .05 and two-sided testing, a sample of 64 is needed in each group to detect a medium effect size of .50 with at least 80% power. This magnitude of effect is considered clinically significant.

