Human Subjects Involvement and Characteristics: One hundred and forty consented veterans and their (non-professional) caregivers will be randomly assigned to one of two study arms: (1) Larval Debridement Therapy (LDT) or (2) Bedside Sharp Debridement (control). The intervention group, or LDT participants, will undergo LDT every 4 days for 2 applications as the main method of debridement strategy. They will have wound samples collected before the initial larvae are applied after 4 days of larval therapy and after 8 days of larval therapy. They will also both be asked to complete a short paper

survey on Days 0, 4 and 8. The subject's wound clinician will also be asked to complete a similar survey (only one round of surveys per consented wound clinician) at Day 0 and Day 8 and 3 months later or at completion of study regarding perceptions of wound debridement therapy.

The control group (bedside sharp debridement) will receive sharp debridement of their wounds 7 days apart x 2 sharp debridements and also have wound samples collected before the initial sharp debridement (Day 0), 4 days after the initial sharp debridement (Day 4), then eight days after initial sharp debridement, which will be 24 hours after the second sharp debridement (Day 8).

Both groups will also receive standard care and therapies ordered by their VA health care providers for their chronic wound care (excluding systemic antibiotics and topical wound antimicrobials), and standard emergency contact numbers. The study duration for the participants is 8 days,

IRB, Safety Committee, Information Security Officer (ISO) and VA R&D committee approval will be obtained prior to beginning this research study. The sample size is anticipated to be 140 total subjects (desired $n=128 + 10\%$ attrition). The desired sample size for data analysis is 128 to achieve adequate sample size for statistical power.

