Setting, Sample: A target goal final sample size of forty adults (plus willing caregivers) from the North Florida Regional Medical Center will be recruited. Including the initial total target of 128 Caregivers and 6 Providers, and accounting for 12 caregivers lost to follow up or 10 subjects who fail screening, the total study recruitment population is still 296 for all recruitment sites. Wound providers and clinicians who care for lower extremity or diabetic foot ulcers will be provided with a "Provider Study Flyer" which gives a brief description of the study with inclusion/exclusion criteria listed (to remind the Provider to approach potentially eligible patients with Research Team Contact information). The clinicians will also be asked to give a Recruitment Brochure to potentially eligible patients (those with lower extremity or diabetic foot ulcers over 8 weeks duration). In addition, study flyers will be sent to select NFRMC wound and podiatry clinics. Providers will be asked to contact study team if any patient is willing to hear about the study. If the patient is willing to hear about the study, they may contact a study team member from the contact number on the recruitment brochure or the provider can let the patient know when the research team member is scheduled to be in the provider clinic office and the patient may talk directly to the research study team member for more information. If patients call a research team member, they will have their questions answered but will not be screened or consented over the phone. They will be scheduled to come into the provider office to discuss the study with a research team member and review informed consent. Members of the research study team will review the informed consent with

the patient and enroll the subject if they agree to participate. Wound clinicians will not be asked to consent subjects, or to provide a list of patients (PHI) to the research team. The subject's wound providers (clinicians) will be the ones to perform the sample collection and apply the LDT or bedside sharp debridement. The study sample also includes one available caregiver of the patient (non-professional) to answer the caregiver surveys if they are willing, and any willing wound care providers, who will be asked to answer the clinician survey regarding perceptions of debridement methods.

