Measurement of IL6. Using techniques such as ELISA and fluorescence resonance energy transfer (FRET) assay methodology, the levels of active IL6 will be calculated and reported.

Methods for Data Collection & Data Management

Variable	Significance	Sampling time	Source	Specific Aim
Age	Demographic	Baseline	EHR	n/a
ABI	Exclusion criterion	Baseline - enrollment	ABI done after ICF	n/a
% nonviable wound tissue	Appearance of wound bed	Baseline Day 0 and Day 8	Provider assessment	Aim 1
Quantitative Cultures (planktonic and biofilm)	Microbial identification	Day 0 (pre-test), + Day 4 and Day 8	Wound samples	Aim 1
Wound Size in cm ² (volume: L x W x D)	Descriptive	Baseline Day 0 and Day 8	Wound measurements	Aim 2
Interleukin 6	Marker of inflammation	Day 0 (pre-test), + Day 4 and Day 8	Wound sample (fluid and/or tissue)	Aim 2
Matrix metalloproteinases (MMP-2 and 9 equivalent)	Elevated MMPs associated with non-healing wounds	Day 0 (pre-test), + Day 4 and Day 8	Wound sample (fluid and/or tissue)	Aim 2
Perceptions of therapy	Perceptions of debridement	Day 0 (pre-test) + Day 8	Patient, Caregiver & Clinician Surveys	Aim 3

Survey Methods

Subjects will be asked to complete a paper survey at Day 0, Day 4 and Day 8 of the study, querying the patient's perceptions of: wound pain, satisfaction with most recent/current wound care method, ease of

care, effectiveness of most recent wound treatment, aesthetics of current wound treatment and toward sharp debridement and maggots for wound care.

Caregivers and wound clinical providers will be asked to complete a paper survey at Day 0 and Day 8 of the study (if wound clinician is caring for more than one study subject, they will be asked to complete a survey at day 0 of first subject, day 8 of first subject and 3 months later or at completion of the study for each type of debridement), querying them about their perceptions of what the patient's experience was regarding the most recent wound debridement methods as well as satisfaction with most recent/current wound care method, ease of care, effectiveness of most recent wound treatment, aesthetics of most current wound treatment and toward sharp debridement and maggots for wound care.

Data Analysis

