Data will be summarized with descriptive statistics. Data will be checked for implausible values, missingness, and distributional form. Data transformations will be made as necessary to achieve normality. To address Specific Aim 1 (comparing the clinical effectiveness of a self-contained larval debridement therapy with a bedside sharp debridement therapy), the numeric outcome measures of changes (post minus pre) in percent of non-viable tissue and bacterial biofilm will be analyzed using independent samples t-tests. To address Specific Aim 2 (comparing wound characteristics of larval debridement and bedside sharp debridement therapies) over time, longitudinal generalized mixed models (GLMMs) will be used with the dependent repeated measures being wound characteristics (e.g., inflammatory markers, wound size) and the independent variable of group assignment (larval versus sharp debridement). To address Specific Aim 3 (investigating patient, caregiver, and clinician perceptions of larval therapy dressings and bedside sharp debridement using self-reported assessments, independent samples t-tests will be used to analyze data measured at the interval level, Wilcoxon rank sum tests will be used to analyze data measured at the ordinal level, and chi-square tests (or Fisher exact tests in the case of data sparseness) will be used to analyze categorical data. All hypotheses testing will be two-sided using a level of significance of .05. Data will be analyzed as "intent to treat." SAS version 9.2 (Cary, N.C.) will be used for all analysis.

Data and Safety Monitoring Plan

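### Aim 3 names only independent-samples tests for clinician perceptions, although about six clinicians apply both debridement methods and some will rate both

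*Combined protocol and SAP*

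**What the plan says.** **Who is randomised.** In section 6, under Human Subjects Involvement, patients and their "caregivers will be randomly assigned to one of two study arms". Clinicians have no arm.

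**Who delivers treatment.** Under Setting, Sample for both sites, the patient's own wound clinicians "perform the sample collection and apply the LDT or bedside sharp debridement".

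**How many clinicians.** The Veteran site text gives the recruitment target as "Including target of 128 Caregivers and 6 Providers". The text for the second site says "the total study recruitment population is still 296 for all recruitment sites".

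**What clinicians are asked, and when.** Survey Methods gives caregivers and clinicians a survey at Day 0 and Day 8. A clinician caring for more than one subject is surveyed at Day 0 and Day 8 of the first subject, and then "3 months later or at completion of the study for each type of debridement". The survey covers the most recent treatment and also "aesthetics of most current wound treatment and toward sharp debridement and maggots for wound care". Human Subjects Involvement adds the limit "only one round of surveys per consented wound clinician". The variables table lists perceptions at Day 0 and Day 8 only.

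**How the ratings are analysed.** In Data Analysis, one Aim 3 sentence covers all three respondent groups: "independent samples t-tests will be used to analyze data measured at the interval level", with rank sum tests for ordinal items and chi-square or Fisher tests for categorical items. Mixed models are named for Aim 2 only.

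**The concern.** Each patient and each caregiver belongs to one arm, so independent-group tests suit comparisons of their ratings between arms. Clinicians are different. When one clinician rates larval therapy and also rates sharp debridement, the two ratings come from the same person and will usually be correlated. An independent-samples test sets that correlation to zero, so its standard error for the difference between methods is wrong.

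The error can go either way. If generous raters are generous to both methods, the test is conservative and the interval wider than it need be. If clinicians who favour one method mark the other down, the test rejects too often. Clinician acceptability is part of the stated study purpose, and the Background names clinician aversion as a reason larval therapy is not chosen, so these ratings are likely to be reported and read.

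**Working it through.** **1. The plan's own figure.** The only power statement is for patients: 64 per arm, effect size 0.50, two-sided 0.05, at least 80% power. The noncentral t gives power 0.801 at 64 per arm and 0.795 at 63, so 64 reproduces. No power, correlation or effect size is given for clinician ratings.

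**2. Number of clinicians.** The site text gives six providers. The total of 296 reproduces as 128 patients + 12 (attrition, 140 - 128) + 128 caregivers + 12 (caregiver loss) + 10 (screen failures) + 6 providers = 296. It is unchanged when the second site is added, so the planned number is still six.

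**3. How often one clinician will see both arms.** 140 / 6 is about 23 patients per clinician on average, so caring for more than one subject is the expected case. Assuming roughly equal allocation, a clinician with 10 patients would see only one arm with probability 2 x 0.5^10 = 0.002.

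**4. Standard error.** Assume unit SD for each method's rating and within-clinician correlation r.

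- Variance of the mean difference with n clinicians: 2(1 - r)/n.
- Variance used by the independent test: 2/n on average.
- Ratio of the independent to the correct standard error: 1/sqrt(1 - r), which is 1.20 at r = 0.3, 1.41 at r = 0.5, 1.83 at r = 0.7 and 0.88 at r = -0.3.

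**5. Type I error and power, n = 6, two-sided 0.05.** Independent test on 10 df, by simulation; paired test on 5 df. The difference is 1 SD for power. Both r and the difference are assumptions.

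| r | Type I error, independent | Power, independent | Power, paired |
|---|---|---|---|
| -0.3 | about 8% | 37% | 24% |
| 0 | 5.0% | 35% | 29% |
| 0.3 | 2.5% | 33% | 39% |
| 0.5 | 1.3% | 32% | 51% |
| 0.7 | 0.4% | 31% | 72% |

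The paired test has type I error 5% throughout. The higher independent-test power at r = -0.3 comes with an inflated error rate and is not a gain.

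**6. Width of the 95% confidence interval.** Independent half-width: 2.228 x sqrt(2/6) = 1.29 SD at any r. Paired half-width: 2.571 x sqrt(2(1 - r)/6) = 1.48 SD at r = 0, 1.24 at 0.3, 1.05 at 0.5 and 0.81 at 0.7.

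**7. Limit set by six raters.** The smallest two-sided exact signed-rank p is 2/2^6 = 0.031, reached only if all six differences go the same way.

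**The case against.** The strongest reply is that the pairing is narrower than it first appears. The survey for each type of debridement applies only to a clinician with more than one subject. The Day 0 and Day 8 surveys concern that clinician's first subject, who is in one arm, and the phrase may govern only the late survey, which the variables table does not list. The limit of one round of surveys per clinician points the same way. On that reading, Day 8 items about the most recent treatment come from different clinicians for each method, and independent-group tests fit them. This stands: the documents do not support the reading that every clinician rates both methods at every survey. It does not remove the point, because the late survey, and the items on attitudes to both methods, still yield two ratings from one person.

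A reader might also infer that the planned tests throw away about half the power. The documents give no correlation or effect size, so they do not support a fixed loss. At a 1 SD difference the relative loss is 15% at r = 0.3 ((0.389 - 0.330)/0.389), 38% at r = 0.5 and 57% at r = 0.7. At r = 0 the paired test is the weaker one. Nor is the direction certain, since negative correlation makes the independent test anti-conservative.

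Finally, a strictly paired test would drop clinicians who rated only one method, and six raters give little power under any test. Both remarks are correct and shape the fix.

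**Conclusion.** The point holds in a limited form. The design lets the same clinician rate both methods, at least at the 3-month or end-of-study survey, and the Aim 3 text offers no analysis that allows for it. For those ratings the planned standard error is wrong: by a factor of 1.20 to 1.83 too large for assumed correlations of 0.3 to 0.7, and too small if the correlation is negative.

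These figures assume six clinicians who all rate both methods, approximately normal ratings with equal SDs, and the correlations and 1 SD difference stated. They illustrate the range and are not a forecast. The effect is confined to the clinician part of Aim 3; the Aim 1 comparison and the 64 per arm are untouched. It is worth correcting because the change is small, not because the trial's main conclusion depends on it.

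**What to change.** Amend the Aim 3 text in Data Analysis as follows.

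- Keep the independent-group tests for between-arm comparisons of patient and caregiver ratings.
- For clinician ratings of both methods, lead with the within-clinician difference and its 95% confidence interval. Use a paired t-test for interval items, the signed-rank test for ordinal items and an exact McNemar test for categorical items.
- If some clinicians will rate only one method, use a mixed model with a clinician random effect so that they are kept.

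In Survey Methods, state at which survey each clinician rates each method and how many ratings per method are expected, and reconcile this with the one-round limit and with the time points in the variables table.

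The cost is a few sentences, with no new data or visits. There is a statistical price: pairing halves the degrees of freedom, from 10 to 5, so a little power is lost if the correlation is near zero (29% against 35% for a 1 SD difference). With six clinicians the text should say that these results are mainly descriptive.

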The primary purpose of this study is to assess the efficacy of larval debridement therapy (LDT) with bagged, sterilized, live, medicinal blow fly (*Lucilia sericata*) larvae (or "BioBags") versus bedside sharp debridement in removing harmful bacteria, biofilm and necrotic tissue from chronic wounds to promote wound healing. Characteristics associated with chronic wound environments will be evaluated through analysis of samples of tissue taken from wound beds before and after both types of debridement. One hundred and forty patients \geq 21 years of age with an open, full thickness wound which is healing by secondary intention (of greater than 8 weeks duration and requires debridement) will be invited to participate. This recruitment number accounts for estimated 10% attrition rate, so final sample number is anticipated to be 128 subjects (64 in each arm). Samples of wound bed tissue and slough tissue (if present) will be collected on Days 0, 4 and 8 or prior to and after each larval debridement intervention or sharp debridement (control). Photos will be taken of the wound bed on Days 0, 4 and 8 or just prior to and after each debridement method. A randomized sampling procedure will place individuals into one of two groups: The intervention group will receive larval debridement therapy once every 4 days for 2 applications (with saline moistened gauze as cover dressing changed daily) and the control group will receive sharp debridement therapy every 7 days for 2 debridements (with wound gel dressing changed daily).

The wound and wound environment will be characterized by assessing wound Matrix Metalloproteinases (MMPs), inflammatory cytokines and the presence of total bacteria, planktonic (free floating) bacteria, and biofilm (sessile) bacteria. Clinicians will be asked to grade the amount of non-viable tissue apparent in the wound bed, appearance of any signs of infection and overall visual appearance of the wound at each visit. Wound size will also be assessed. Subjects will be asked to rate their wound related pain level at each visit before and after the debridement method is applied. Subjects, caregivers and clinicians will be asked to complete a short survey to self-report their perceptions of each method of debridement. Data will be analyzed using bivariate and multivariate methods.

4. **Background:**

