Chronic wounds are a significant health problem in the U.S.. Chronic wounds are defined as wounds that have "have failed to proceed through an orderly and timely reparative process to produce anatomic and functional integrity." Health care costs related to the management and treatment of chronic wounds in the U.S. exceeds \$20 billion annually. For many health care providers, the treatment and management of non-healing wounds is challenging. Traditionally, basic wound care has consisted of surgical debridement, manual irrigation, moisture retentive dressings, and topical and/or systemic antimicrobial therapy. Although there has been tremendous progress in the science of

wound healing, the prevalence and incidence of chronic wounds and their associated complications continues to escalate.

The presence and complexity of bacterial biofilms in chronic wounds has recently been recognized as a key aspect of non-healing wounds. Bacterial biofilms are sessile colonies of polymicrobial organisms (bacterial, fungal, and possibly, viral) which are often symbiotic. These biofilm colonies produce a protective coating to protect the colonies from host defenses. The character of this protective substance which is unique to biofilms is dynamic and production of its components seems to be triggered by hostile environments in the wound bed (such as the presence of topical antibiotics). Biofilms have been shown to have survival and defense mechanisms that: 1) inhibit the healing aspects of inflammatory cells; 2) resist antibiotics (topical and systemic) and other therapies; and 3) initiate cell to cell communication pathways (quorum sensing) which facilitate new biofilm growth, resulting in recalcitrant non-healing wounds.

Wound larval debridement therapy (LDT) has been shown to have promise in healing chronic wounds by eradicating biofilms. Recently (2012), the PI was part of a team of investigators who collaborated with the University of Florida Wound Research Laboratory and conducted several in vitro experiments to demonstrate the efficacy of larval exposure to biofilm (Cowan et al., 2013). These studies demonstrated bacterial biofilm (*Pseudomonas aeruginosa* (PA01) bacteria and *Staphylococcus aureus* (SA35556) bacteria) grown on pigskin explants were completely eradicated within 48 hours of exposure to loose medicinal maggots from Monarch Labs (larvae).

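### The Aim 1 biofilm outcome is a CFU change whose scale, and whose order of transforming and differencing, are not fixed; differencing first would put power for a proportional effect below 80%

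*Combined protocol and SAP*

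**What the plan says.** Specific Aim 1 (section 5) lists two comparisons. One is the visual reduction of non-viable tissue; the other is "The reduction in colony forming units (CFU) of bacterial biofilm in samples taken from the wound bed". Section 6, under Measurement of bacterial colonization, obtains the counts by serial dilution and plating. Neither place mentions a log scale or a proportional reduction.

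Section 6, Data Analysis, first says that data will be checked for distributional form, and then: "Data transformations will be made as necessary to achieve normality". It next gives the Aim 1 test: "the numeric outcome measures of changes (post minus pre) in percent of non-viable tissue and bacterial biofilm will be analyzed using independent samples t-tests". It does not say which variable is transformed, by what function, whether before or after subtraction, or what happens to a zero count. Nor does it say which visit is the post value; the data collection table has cultures on Days 0, 4 and 8.

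The sample size statement, given in the same terms for both sites, asks for 64 per arm at a two-sided .05 level "to detect a medium effect size of .50 with at least 80% power". For the Veteran site its stated basis is: "Power analysis is based on the patient sample and the primary study aim of comparing debridement methods on clinical effectiveness". No outcome, unit or standard deviation is attached to the .50.

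**The concern.** Plate counts from serial dilutions can span orders of magnitude, and a debridement effect on them is naturally thought of as a proportion removed. An arithmetic difference of such counts mostly reflects how heavily the wound was colonised at Day 0:

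- 10^7 falling to 10^6 (90% removed) is a change of -9,000,000.
- 10^5 falling to 10^4 (also 90% removed) is a change of -90,000.
- 10^5 falling to 10^2 (99.9% removed) is a change of -99,900.

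The first wound counts 100 times as much as the second for the same proportional result, and about 90 times as much as the third, which did better.

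A normality rule applied after subtraction cannot undo this. The difference can take either sign, so it cannot be logged. Signed logs, cube roots and ranks still order wounds largely by baseline load. The order of the two steps therefore decides what is being tested, and the plan leaves it open. At stake is one of the two outcomes of the aim that the sample size rests on, and the one closest to the gap in quantitative biofilm evidence that the Purpose Statement describes.

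Zero counts add to the problem. The Background reports complete eradication of biofilm in vitro, so counts below detection are possible, and the log of zero is undefined without a rule.

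**Working it through.** **1. The plan's own figure.** Inputs from Sample Size Power Analysis: d = 0.50, two-sided alpha .05, 64 per arm. The normal approximation is n = 2(1.96 + 0.8416)²/0.50² = 2(7.849)/0.25 = 62.8, so 63. The exact noncentral t gives n = 63.77, so 64, with power 0.8015 at 64 per arm. The stated figure reproduces.

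**2. Power by order of operations.** The documents give no CFU mean, SD or expected fall, so these are assumed. Day 0 log10 CFU is normal with mean 6 and SD 0.25 to 1.5. The log10 change is normal with SD 0.25 to 1.5. The mean control fall is 0 to 2 log10. The larval arm falls a further 0.5 SD of log10 change. There are 64 per arm, no counts below detection, and 3,000 simulated trials in each of 4 × 4 × 4 = 64 combinations. The Monte Carlo standard error near 0.80 is √(0.8 × 0.2/3000) = 0.007.

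Each simulated trial was analysed in five ways. In the columns below, A is log10 at each visit, then difference; B is the untransformed difference; C is the signed log of the difference; D is its cube root; E is its ranks.

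| SD Day 0 | SD change | Control fall | A | B | C | D | E |
|---|---|---|---|---|---|---|---|
| 0.25 | 0.25 | 0 | 0.80 | 0.62 | 0.65 | 0.71 | 0.72 |
| 0.5 | 0.5 | 0.5 | 0.82 | 0.16 | 0.41 | 0.40 | 0.31 |
| 1.0 | 1.0 | 0 | 0.79 | 0.07 | 0.64 | 0.48 | 0.58 |
| 1.0 | 1.0 | 1.0 | 0.80 | 0.03 | 0.40 | 0.22 | 0.20 |
| 1.5 | 1.5 | 1.0 | 0.81 | 0.02 | 0.47 | 0.19 | 0.28 |
| 1.5 | 1.0 | 2.0 | 0.79 | 0.01 | 0.08 | 0.04 | 0.07 |

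Over all 64 combinations, A stays at 0.79-0.82, B runs from 0.01 to 0.62, and C to E run from 0.04 to 0.72. Values under 0.05 for B arise because extreme skewness makes the t-test conservative.

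A second set of runs used correlated pre and post counts, SD 0.25-2.0 and a control fall of 0 to 1 log. It gave 1-65% for B. With correlation .5, C to E gave 6-71%. No route that differences first reached 80%.

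**3. Limits of logging first.** Assume SD 1, correlation .5 (so the SD of change is √(2(1 - 0.5)) = 1), a detection limit of 2 log10, and half the limit substituted below it. For a control fall of 3 logs, the Day 8 means are 3.0 (control) and 2.5 (larval). The expected shares below detection are Φ(2 - 3.0) = 16% and Φ(2 - 2.5) = 31%.

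| Control fall | Below limit: control / larval | Power |
|---|---|---|
| 3 logs | 16% / 31% | 71% |
| 4 logs | 50% / 69% | 35% |
| 5 logs | 84% / 93% | 8% |

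The substituted value matters too. With 25% and 43% of final counts below the limit, power ran from 51% to 79% depending only on what was substituted.

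**The case against.** The best defence is textual. The plan never says that CFU are analysed untransformed. The transformation sentence speaks of data in general and comes before the Aim 1 test, so a statistician could log the counts at each visit and then take post minus pre without departing from the text. That stands. A reader might infer that the plan commits to a t-test on untransformed CFU differences; the documents do not support that. They permit it, and it is the more direct reading, because the variable the t-test needs to be near normal is the change.

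A reader might also infer that the stated 80% power is lost. It is not: it is power for a standardised .50 on an unnamed scale, and it reproduces. The loss appears only under the difference-first reading with a proportional effect, and its size depends on CFU variability that the documents do not give. Very low figures such as 1-3% belong to one part of the assumed range.

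A third inference would be that the open rule inflates type I error. Taking the smallest of several p-values would do so, to roughly 9-13% for four candidate analyses in simulation. But the written rule ties the transform to normality, not to significance, so that figure describes misuse of the plan and not the plan.

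Finally, logging first is not immune to trouble. With heavy censoring its power falls as well, and log change then also tracks baseline load. That stands, and is the reason for a detection-limit rule.

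**Conclusion.** The point holds as under-specification of a primary-aim outcome. The plan fixes neither the scale of the biofilm change nor the order of transforming and differencing, and the choice is material. For a true proportional effect of 0.5 SD on log10 change at 64 per arm, logging at each visit and then differencing gives about 80%. Differencing first gives about 1-65% untransformed, or about 4-72% after a later transform or ranking.

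This rests on lognormal counts, a proportional effect and assumed CFU variability. The 80% for logging first also assumes few counts below detection. The sample size calculation is not in error, and percent non-viable tissue is not touched by the argument.

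**What to change.** In section 6, Data Analysis, replace the biofilm part of the Aim 1 sentence with wording to this effect: *Biofilm CFU will be converted to log10 at each visit. The outcome is Day 8 log10 CFU minus Day 0 log10 CFU, compared between arms by an independent-samples t-test and reported as a ratio of geometric means with its confidence interval.*

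In addition:

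- State that the open transformation rule does not apply to this outcome.
- Pre-specify the handling of counts below the detection limit at any visit, for example a fixed substitution (such as half the limit) with a censored regression as sensitivity analysis. Give the laboratory's limit, and note that heavy censoring would lower power.
- In both Sample Size Power Analysis paragraphs, state that for biofilm the .50 refers to the SD of log10 change.

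Settle this before the data are analysed. The cost is wording only: no change in sample size, sampling or laboratory work. The small downside is that the effect is reported as a fold change and not as a CFU difference.
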